6.1. Product Presentation, Storage and Expiry

6.1.1. Investigational Medicinal Product (IMP): BPL HRIG

BPL HRIG is a liquid concentrate of rabies human immunoglobulin. BPL HRIG is obtained from blood from screened donors, who are selected from within the United States of America. BPL HRIG is manufactured, packed and labelled by the sponsor according to the requirements of FDA CFRs, Directive 2001/20/EC and Good Manufacturing Practice.

BPL HRIG is presented in 5 ml glass vials, each of which is packed in a carton. The concentration of specific IgG to Rabies virus is not less than 150 IU/mL solution for injection in nominal 500 IU vials. The actual fill volume will be printed on the vial label. The shelf-life of BPL HRIG is specified in the Investigator's Brochure. The expiry date is printed on the vial label and carton; product must not be used beyond the expiry date. Dosing for BPL HRIG will be based on the actual potency (see pharmacy manual).

Vials of BPL HRIG should be stored in the original container at 2°C to 8°C (36°F to 46°F). Storage for up to one week at 25°C (77°F) in the original container is not detrimental. DO NOT FREEZE. Store in the original vial. Keep vial in the outer carton to protect from light. The product should be brought to room or body temperature before use.

The colour can vary from colourless to pale-yellow and is either clear or slightly opalescent. Do not use solutions that are cloudy or have deposits.

Further information can be found in the Investigator's Brochure.

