6.1.2. Comparator HRIG

FDA-approved HRIG comparator HyperRAB® S/D will be presented in 10 mL vials, at a nominal potency of 150 IU/mL. Dosing for HyperRAB® S/D will be based on the actual potency (see pharmacy manual).

Vials of HyperRAB® S/D should be stored at 2°C to 8°C (36°F to 46°F). DO NOT FREEZE. The expiry date is printed on the vial label; product must not be used beyond the expiry date.

Further information can be found in the approved Prescribing Information, [Appendix D](#).

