6.2. Randomized Treatment

Subjects will be randomized to receive one of two treatments described below.

Treatment A: BPL HRIG + rabies vaccine (RabAvert®).

A 20 IU/kg dose of BPL HRIG will be given on Day 0 via IM injection. The volume to be injected will be based upon the subject's weight on Day 0 and BPL HRIG actual potency (see pharmacy manual). A maximum of 5 mL will be administered to each lateral thigh and a maximum 2.0 mL to the deltoid muscle. The gluteal muscle will not be used for IM injection due to the increased variability of absorption from this injection site and the risk of injury to the sciatic nerve.

The total volume will be split between the injection sites as follows:

Table 5: Treatment A -total volume to be split between the injection sites

Injection number	Volume to be injected	Site of injection
1	up to 5 mL depending on bodyweight	left lateral thigh muscle
2	up to 5 mL depending on bodyweight	right lateral thigh muscle
3 (if required)	up to 2 mL depending on bodyweight	left deltoid muscle

A 1.0 ml dose of active vaccine (2.5 IU/ml) will be given IM on 5 occasions: on Days 0, 3, 7, 14, and 28. On day 0, the vaccine will be administered to the right deltoid muscle. The subsequent doses of vaccine on days 3, 7, 14, and 28 may be administered to the right or the left deltoid muscle.

The vaccine dose should never be administered into the same anatomical site as the HRIG.

Treatment B: FDA-approved comparator HRIG (HyperRAB[®] S/D) + rabies vaccine (RabAvert[®])

A 20 IU/kg dose of comparator HRIG will be given on Day 0 via IM injection. The volume to be injected will be based upon the subject's weight on Day 0 and BPL HRIG actual potency (see pharmacy manual). A maximum of 5 mL will be administered to each lateral thigh and a maximum 2.0 mL to the deltoid muscle. The gluteal muscle will not be used for IM injection due to the increased variability of absorption from this injection site and the risk of injury to the sciatic nerve.

The total volume will be split between the injection sites as follows:

Table 6: Treatment B -total volume to be split between the injection sites

Injection number	Volume to be injected	Site of injection
1	Up to 5 mL depending on body weight	left lateral thigh muscle
2	up to 5 mL depending on bodyweight	right lateral thigh muscle
3 (if required)	up to 2 mL depending on bodyweight	left deltoid muscle

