6.3. Product Administration

HRIG will be drawn into 2 or 3 (as appropriate according to the calculated volume) 5.0 mL syringes and injected to the lateral thighs and, if required, the left deltoid muscle.

Vaccine will be drawn into a 1.0 mL syringe and injected to the right deltoid muscle.

The selection of HRIG products to be administered (BPL HRIG or comparator HRIG) as per the randomized treatment, the calculation of the volume to be administered, and the drawing up of the appropriate volume into syringe(s), will be performed by the unblinded pharmacist/or licensed medical personnel. The selection of products to be administered, calculation of volume to be administered, and the volume in the syringe will be checked by the unblinded nurse administrator prior to administration to the subject.

For the BPL HRIG, comparator HRIG, the following details will be recorded:

- name of product
- lot number

-
- total dose required in IU, calculated from body weight (20 IU/kg)
 - total dose required in mL, calculated from the actual potency
 - for each specified injection site, actual dose administered in mL (this should not exceed 5.0 mL for each lateral thigh muscle and 2.0 mL for the left deltoid muscle)
 - date and time of injection on Day 0

See the pharmacy manual for additional information on calculations, potency and details to be recorded. Certificates of analysis for both products will be kept in BPL files.

For the rabies vaccine, the following details will be recorded:

- name of product
- lot number
- confirmation of actual dose given in mL (this should be 1.0 ml)
- date, time, and location of injection, on Days 0, 3, 7, 14, and 28

See the pharmacy manual for additional information on details to be recorded. For any given subject, every effort must be made to use the same lot of active rabies vaccine throughout the study.

For additional details on administration of BPL and comparator HRIG using actual potency versus nominal potency refer to [Appendix F](#) and the pharmacy manual.

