8.2.9. Physical Examination

A physical examination will be performed at the Screening Visit, on Day 49, and at the End-of-Study Assessment. The following body systems will be examined: Head, ears, eyes, nose, throat, chest, cardiovascular, respiratory, abdomen, musculoskeletal, skin and general appearance.

In addition, a 12-lead ECG in a semi-recumbent position following at least 5 minutes of rest will be performed at Screening and the End-of-Study Assessment. Results at the Screening Visit will be used to determine eligibility for the study. Based upon the investigator's judgement, significant abnormalities will exclude the subject from the study.

Any changes in physical examination or ECG from the Screening assessment will be recorded, and any adverse changes will be reported as adverse events.

Body weight and height will be measured at Screening, and body weight only will be repeated pre-dose on Day 0 and at the End-of-Study Assessment. Body weight at Screening or Day 0 which exceeds 95.5 kg will exclude the subject from the study.

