10.4. Analysis Populations

The following analysis populations will be defined for this study.

Intent-to-Treat (ITT) Population

The intent-to-treat (ITT) population will include all randomized subjects. All analyses will be performed using the ITT population.

Safety Population

The safety population will be defined as all subjects who receive at least one dose of BPL HRIG / comparator HRIG. Safety data will be analyzed up to the point of withdrawal for applicable subjects. The safety population will be used for all safety analyses.

Per Protocol Population

The per protocol population will be split into the primary and secondary PK populations.

The **primary PK population** will be defined as all subjects who receive the full dose of BPL HRIG / comparator HRIG and the first 3 doses of active rabies vaccine on Visits 2, 3, and 5, and for whom the PK sample at Visit 6 is taken. This population will be used for the primary PK analysis and selected secondary analyses.

The **secondary PK population** will be defined as all subjects who receive the full dose of BPL HRIG / comparator HRIG and all 5 doses of active rabies vaccine and for whom all required PK samples are taken. This population will be used for selected secondary PK analyses and the exploratory PK analysis.

Subjects with a pre-dose RVNA of \geq the LLOQ will be excluded from all analyses.

Subjects not meeting eligibility criteria or for whom major protocol deviations are reported may be excluded from the per protocol population if considered to potentially impact on the PK analysis. Any such cases will be fully justified in the clinical study report.

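### At the minimum or nominal potency of 150 IU/mL, the 20 IU/kg dose, the 95.5 kg weight limit and the 12 mL site total do not agree for subjects above 90 kg

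*Protocol*

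**What the plan says.** **Dose.** Protocol section 6.2 sets the same weight-based dose in both arms: "A 20 IU/kg dose of BPL HRIG will be given on Day 0 via IM injection" and "A 20 IU/kg dose of comparator HRIG will be given on Day 0 via IM injection".

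**Sites.** The same section gives the volume limits: "A maximum of 5 mL will be administered to each lateral thigh and a maximum 2.0 mL to the deltoid muscle". Tables 5 and 6 list three HRIG sites: left thigh, right thigh and, if needed, left deltoid. Section 6.3 repeats the limits for the volume recorded at each site: "this should not exceed 5.0 mL for each lateral thigh muscle and 2.0 mL for the left deltoid muscle". There is no fourth HRIG site. Section 6.2 rules out the gluteal muscle and gives the right deltoid to the Day 0 vaccine, and section 7.3.2 requires vaccine and HRIG to go to separate sites.

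**Weight.** Exclusion criterion 5.3(s) applies above 95.5 kg, and section 8.2.9 confirms it: "Body weight at Screening or Day 0 which exceeds 95.5 kg will exclude the subject from the study". A subject weighing exactly 95.5 kg is therefore eligible.

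**Potency.** Section 6.1.1 gives a floor for BPL HRIG: "The concentration of specific IgG to Rabies virus is not less than 150 IU/mL solution for injection in nominal 500 IU vials". Section 6.1.2 gives a nominal value for the comparator: "presented in 10 mL vials, at a nominal potency of 150 IU/mL". Sections 6.1.1, 6.1.2 and 6.3 and Appendix F base the volume on actual lot potency and refer to the pharmacy manual for detail. The only actual-potency figure in the documents is the 230 IU/mL in Appendix F's worked example.

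**Analysis.** Section 10.4 defines the primary PK population as "all subjects who receive the full dose of BPL HRIG / comparator HRIG and the first 3 doses of active rabies vaccine", with further conditions. SAP section 7b repeats this. Under protocol section 10.7.2, a subject without the full HRIG dose is a non-complier.

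**The concern.** The weight limit, the dose and the site limits together imply a lowest usable lot potency. That potency is higher than the BPL floor and higher than the comparator's nominal value, and the protocol does not state it. For a lot that the protocol admits, some eligible subjects cannot receive the stated dose within the stated volumes, and the protocol has no rule for a calculated volume above the total.

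The order of events makes this a matter for the analysis as well as for the pharmacy. Weight is checked against the limit before randomization (section 7.3.1). Unblinded staff calculate the volume for the assigned product (section 6.3), and sections 2.9 and 6.6 say that volumes differ between products. An overflow would therefore come to light after assignment. A subject then held to the limits would drop out of the population used for the primary analysis (section 10.5.1), for a reason tied to body weight and possibly to the product. In the runs of section 10.7.2 the same subject would be counted as a failure once and as a success once. One subject in an arm of 81 is 1/81, or about 1.2 percentage points, against a margin of 10 points.

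**Working it through.** **Inputs**
- Dose 20 IU/kg (section 6.2)
- Highest eligible weight 95.5 kg (sections 5.3(s), 8.2.9)
- Site limits 5, 5 and 2 mL (sections 6.2, 6.3)
- Potency 150 IU/mL as floor or nominal value (sections 6.1.1, 6.1.2)
- Potency 230 IU/mL as an example (Appendix F)

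**Formulas**
- Volume = weight × 20 / potency
- Highest weight that fits = site total × potency / 20
- Lowest potency that fits = highest weight × 20 / site total

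**1. The plan's own example.** Appendix F: 75 × 20 = 1500 IU; 1500 / 230 = 6.52 mL. The stated 6.5 mL reproduces, so the volume formula is the one the protocol intends.

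**2. Site total.** 5 + 5 + 2 = 12 mL.

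**3. Largest dose.** 95.5 × 20 = 1910 IU.

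**4. At 150 IU/mL.** 1910 / 150 = 12.73 mL, which is 0.73 mL over the total. The highest weight that fits is 12 × 150 / 20 = 90 kg.

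**5. If the volume is held to 12 mL at 150 IU/mL.** 12 × 150 = 1800 IU; 1800 / 95.5 = 18.85 IU/kg; 1 − 1800/1910 = 5.8% short.

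**6. Potency at which all the figures agree.** 1910 / 12 = 159.2 IU/mL, which is 6.1% above 150.

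**7. By actual potency.** The rows for 155 and 160 are illustrative; the documents give no actual lot potency apart from the example.

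| Actual potency (IU/mL) | Volume at 95.5 kg (mL) | Highest weight within 12 mL (kg) | Eligible weights affected |
|---|---|---|---|
| 150 | 12.73 | 90.0 | above 90 to 95.5 kg |
| 155 | 12.32 | 93.0 | above 93 to 95.5 kg |
| 159.2 | 12.00 | 95.5 | none |
| 160 | 11.94 | 96.0 | none |
| 230 (Appendix F example) | 8.30 | 138.0 | none |

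**Adjacent text.** The Treatment B paragraph of section 6.2 bases the comparator volume on the potency of BPL HRIG, while section 6.1.2 and Appendix F point to the comparator's own potency. This changes which potency enters the formula for that arm, so it belongs in the same reconciliation.

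**The case against.** The strongest reply is that 150 IU/mL is not the dosing potency for either product. It is a floor for one and a nominal value for the other, and volume is calculated from the actual lot. A lot only 6.1% above 150 fits every eligible weight, and the single actual potency in the documents, 230 IU/mL, leaves ample room. The pharmacy manual and the lot certificates may show that no supplied lot is near 150, or may say how to handle an overflow. This stands. A reader might infer that the limits can never hold together; the documents do not support that, because they agree for any lot at or above 159.2 IU/mL. The reply does not remove the point. Eligibility, site limits and analysis populations are set in the protocol, and the protocol admits lots on which they disagree.

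A second reply is that losing the subject is not inevitable. If the site limit were exceeded, the full dose would have been given, and section 10.4 makes exclusion for a major deviation discretionary. Section 10.4 also calls for all analyses in the ITT population, and section 10.7.2 pairs the worst case with a best case. This stands too. It limits the consequence to subjects actually held to 12 mL, and those subjects remain in the ITT analysis.

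A reader might also infer that the loss falls on one arm, or that the worst-case run would favour BPL HRIG. Neither is supported. Sections 2.9 and 6.6 say that volumes differ, but not by how much or in which direction. Both arms, one arm or neither could be affected. If it were the BPL arm, the worst-case run would move against BPL HRIG.

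**Conclusion.** The point holds as a conditional inconsistency. For lots from 150 to just under 159.2 IU/mL, the protocol's dose, weight limit and site limits cannot all be followed for the heaviest eligible subjects. The largest excess is 0.73 mL, or a dose 5.8% short if the volume is held to 12 mL, both at 95.5 kg and exactly 150 IU/mL. The affected band narrows as potency rises and is empty from 159.2 IU/mL upward.

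This rests on three things: that 12 mL is a firm total, as the two statements of the limits indicate; that a lot in that potency range is supplied, which the documents neither show nor rule out; and that the pharmacy manual, which was not available, does not already settle the matter.

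The number of subjects affected cannot be estimated, because the documents give no weight distribution and no lot potencies. Section 10.9 leaves 81 − 73 = 8 subjects per arm for losses. A reader might infer a threat to power from that, but nothing in the documents shows how much of the allowance this would use. What can be said is that any loss would follow randomization, would be selective on weight and could differ between arms.

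**What to change.** Reconcile three sets of statements so that every eligible weight can receive the stated dose within the stated volumes with every lot supplied:
- the weight limit (protocol sections 5.3(s) and 8.2.9);
- the site limits (sections 6.2 and 6.3);
- the potency statements (sections 6.1.1 and 6.1.2 and Appendix F), including the potency named for the comparator in section 6.2.

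Alternatively, state in the protocol the lot potency on which the existing figures agree. Which figure changes is for the sponsor; no dose, volume limit or eligibility rule is proposed here.

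The cost is a wording amendment. If all lots of both products are already at or above 159.2 IU/mL, one sentence saying so, consistent with the pharmacy manual, closes the point. No change to the sample size or the analysis method is needed.

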6.3. Product Administration

HRIG will be drawn into 2 or 3 (as appropriate according to the calculated volume) 5.0 mL syringes and injected to the lateral thighs and, if required, the left deltoid muscle.

Vaccine will be drawn into a 1.0 mL syringe and injected to the right deltoid muscle.

The selection of HRIG products to be administered (BPL HRIG or comparator HRIG) as per the randomized treatment, the calculation of the volume to be administered, and the drawing up of the appropriate volume into syringe(s), will be performed by the unblinded pharmacist/or licensed medical personnel. The selection of products to be administered, calculation of volume to be administered, and the volume in the syringe will be checked by the unblinded nurse administrator prior to administration to the subject.

For the BPL HRIG, comparator HRIG, the following details will be recorded:

- name of product
- lot number

-
- total dose required in IU, calculated from body weight (20 IU/kg)
 - total dose required in mL, calculated from the actual potency
 - for each specified injection site, actual dose administered in mL (this should not exceed 5.0 mL for each lateral thigh muscle and 2.0 mL for the left deltoid muscle)
 - date and time of injection on Day 0

See the pharmacy manual for additional information on calculations, potency and details to be recorded. Certificates of analysis for both products will be kept in BPL files.

For the rabies vaccine, the following details will be recorded:

- name of product
- lot number
- confirmation of actual dose given in mL (this should be 1.0 ml)
- date, time, and location of injection, on Days 0, 3, 7, 14, and 28

See the pharmacy manual for additional information on details to be recorded. For any given subject, every effort must be made to use the same lot of active rabies vaccine throughout the study.

For additional details on administration of BPL and comparator HRIG using actual potency versus nominal potency refer to [Appendix F](#) and the pharmacy manual.

6.4. Concurrent Medication

Concomitant medication is defined as any medication, other than the study drug, which is taken during the trial, including prescription and over-the-counter medicines. For the purposes of the study, nutritional supplements including vitamins and minerals are not considered concomitant medications. The generic names of medications should be used where possible.

Concomitant medication will be recorded in the subject notes with indication, dose information, and dates of administration. Any new medications taken or any changes to the form, frequency or dose of existing medication occurring during the study will also be recorded.

Corticosteroids, other immunosuppressive agents or treatments, and immunosuppressive illnesses can interfere with the development of active immunity and, in patients exposed to the rabies virus, predispose the patient to developing rabies. Immunosuppressive agents should not be administered during the study, unless essential for the treatment of other conditions. Oral or IV steroids should not be taken within 14 days prior to Day 0, and if required during the study the subject will be withdrawn from the study. Topical or inhaled steroids are permitted.

Other antibodies in the BPL HRIG or comparator preparation may interfere with the response to live vaccines such as measles, mumps, polio or rubella. Therefore, immunization with live

vaccines should not be given within 3 months of BPL HRIG administration. Inactivated Influenza vaccination is allowed, see Investigator Brochure.

6.5. Drug Accountability

The investigator is responsible for ensuring that a record is maintained for every vial of study medication and licensed product provided to the site for the study. **Accounts must be kept for each subject of the identity (lot#) and number of vials administered, used and returned to pharmacy, to demonstrate full drug accountability.** The unblinded staff at the study center will confirm receipt of the study supplies, indicating dates of receipt, expiration dates, temperature conditions, lot numbers and quantities of all study supplies received from the Central Drug Distributor. Records will be kept of medication administered to each subject, as well as amounts remaining at the study conclusion. The study monitor will arrange for the collection of unused supplies for return to the Sponsor / Central Drug Distributor upon completion of the study or before if appropriate. Alternatively, if a documented drug destruction policy exists; unused supplies may be destroyed at the investigational site.

The following records will therefore need to be maintained to provide complete accountability:

- Dispatch notes or invoice slips
- Receipt forms
- Dispensing log
- Returns to BPL / Central Drug Distributor OR destruction logs

It is essential that all study product administered to the subject is recorded in the subject's clinic notes including amount administered.

Used and partly used vials will be retained at the pharmacy and reserved for drug accountability purposes, until written confirmation is received from the monitor that they may be disposed of locally.

The products provided for the study must be used solely as indicated in the protocol and must never be used for subjects not participating in the study.

A log of daily temperatures in the pharmacy storage area must be maintained to demonstrate that the products have been stored under the specified conditions.

6.6. Randomization and Blinding

Subjects will be assigned to one of the treatment groups according to a randomization schedule prepared before the study start. Each subject's randomization number will correspond to the treatment assigned. Therefore, subjects and investigators will be blinded to the treatment received.

An unblinded pharmacist or licensed medical personnel will be responsible for preparing study treatments in accordance with the randomized treatment assignment. As the volume differs between the HRIGs, the staff responsible for administration of the treatment will be unblinded. Different, blinded study personnel will be responsible for observing any reactions and interviewing subjects about potential reactions.

Information on roles and responsibilities of blinded and unblinded study personnel will be detailed in the Blinded Project Plan.

